These recruited individuals will be considered as wave 1 of recruitment and will each receive 10 additional coupons to recruit the members of their networks. The next round of individuals recruited and enrolled will be considered as wave 2, and so on. The number of 10 coupons was selected to avoid a bias risk related to participation incentives.

To facilitate the return of HIVST kit results, participant will upload the picture of results labeled with their identifier directly using the link of the external website that they received from community worker/research team during their visits at pharmacy. In case of any question, they could reach community worker/research team by hotline number. According to the results, the participants will be proposed with a support for linkage to confirmatory test or to PrEP services. Each non-reactive participant will be provided another new coupon (paper or electronic format upon their preference) with a reminder to perform a 6-monthly HIV testing during 18 months. They will not be granted any token or incentives if they fail to return the result of HIVST kit taken at pharmacies. These incentives are also added upon the number of recruited members of their networks using common money transfer and payment services in Cambodia such as Wing, TrueMoney.

After 6 months, a qualitative assessment will be conducted to evaluate feasibility, acceptability and appropriateness of the intervention and to identify barriers and facilitators.

Several ART sites/HIV clinics particularly in charge of key populations will be specifically selected as participating centers in order to collect information on linkage to care or prevention services for positive and negative participants, respectively.

Tentative study agenda

- Protocol submission: December 2022
- Study implementation: February 2023 July 2023
- Data collection: August 2023 April 2025 (18 months)
- Duration of the study: 24 months

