7 STUDY ENDPOINTS

Primary endpoint

 HIV self-testing uptake defined as the number of HIV self-tests delivered / total number of coupons distributed

Secondary endpoints

- Proportion of HIVST result's recorded / total number of HIVST delivered
- Proportion of paper and electronic coupons delivered
- Number of HIV tests realized / number of HIV tests results non recorded
- Proportion of MSM/TGW with positive HIV self-tests linked to an ART site
- Proportion of negative MSM/TGW linked to PrEP services
- Characteristics of participants recruited (sociodemographic, sexual behavior, utilization of dating application, substance use) in comparison with IBBS 2019 report
- Proportion of participants with 6-monthly repeated HIV testing during 18 months

Outcomes of acceptability and appropriateness will be explored during focus groups: comfort, usefulness, suitability, confidentiality, credibility, advantages and barriers.

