8 STRATEGIES AND TREATMENTS

Strategies and Treatments used in the study

The study does not involve with any direct medical treatment. However, intervention after delivering HIV test results will be proposed as follow:

In case of reactive HIV test, the participant could join immediately one research team by hotline and messages on the website that will provide support and orientation. After 1 week, contact with the participant will be done by phone by the research team to confirm the linkage to one of the partner ART sites. The linkage between participants and HIV clinics will be done by the initial QR code.

If the linkage to confirmatory testing and/or care is not confirmed, we will propose to participant additional help of a community worker.

Version 1.1 du 18/04/2022

 In case of non-reactive test, the participant could download in the external website one electronic coupon (QR code) to repeat the HIV test every 6 month. Participants will be informed on the external website about the possibilities to join the pilot PrEP program in Chhouk Sar clinic in Phnom Penh.

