14 STATISTICAL ANALYSES

Calculation of number of participants needed

We will use a pragmatic approach with the objective to recruit the maximum of MSM and TGW. According to the IBBS 2019, the estimated number of MSM in Phnom Penh is 6300 and the

Version 1.1 du 18/04/2022

estimated number of TGW is 1400.

With 1500 participants (1000 MSM and 500 TGW), we will be able to estimate an HIV self-test uptake of 70% to within a 95% confidence interval of +/- 2 – 2.5% (width of the confidence interval (in %) = $1.96 \times \sqrt{(p \times (1-p)/n)}$.

Analysis plan

Description of the characteristics at inclusion.

These variables will be described by their median, interquartile range, mean, standard deviation, or frequencies (%), as appropriate. These variables will be compared to those reported in the IBBS 2019 for MSM and TGW.

Primary outcome

The percentage, and its 95% confidence interval of HIV self-tests delivered among the total number of coupons distributed will be given and stratified by gender (MSM or TGW) and by type of coupons (paper or electronic).

Secondary outcomes

- The percentage and its 95% confidence interval of HIVST result's recorded among the total number of HIVST delivered will be given and stratified by gender (MSM or TGW)
- For those accepting to be contacted by phone, the percentage and its 95% confidence interval of HIVST realized among the number of HIV tests results non recorded will be given
- The percentage and its 95% confidence interval of participants with positive HIV selftests linked to an ART site will be given and stratified by gender (MSM or TGW)
- The percentage and its 95% confidence interval of participants with negative HIV selftests linked to PrEP services will be given and stratified by gender (MSM or TGW)
- The percentage and its 95% confidence interval of participants with 6-monthly repeated HIV testing during the 18 months (so 4 HIVSTs during the total duration of the study) will be given
- The probability of discontinuation of HIV testing and its 95% confidence interval, as well as the median time to the occurrence of HIV testing discontinuation, will be determined using a Kaplan Meier analysis, to take into account censored data due to lost of follow-up.

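### The primary uptake ratio does not separate peer-recruitment coupons and first kits from the 6-monthly repeat coupons and kits, so it mixes peer uptake with retention

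*Protocol*

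**What the plan says.** Protocol section 7 defines the primary endpoint as "HIV self-testing uptake defined as the number of HIV self-tests delivered / total number of coupons distributed". The summary in section 1 repeats this. Section 14 plans the percentage and "interval of HIV self-tests delivered among the total number of coupons distributed will be given and stratified by gender", and also by paper or electronic coupon. Those are the only strata.

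Two kinds of coupon lead to a kit:

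- **Recruitment coupons.** Each seed receives 10 (section 5, Study overview), and recruited participants "will each receive 10 additional coupons to recruit the members of their networks".
- **Repeat coupons.** Section 5 states: "Each non-reactive participant will be provided another new coupon (paper or electronic format upon their preference) with a reminder to perform a 6-monthly HIV testing". Section 8 says that after a non-reactive result "the participant could download in the external website one electronic coupon (QR code) to repeat the HIV test every 6 month". Section 9 repeats the electronic download, and its list for the pharmacy visit also mentions a further coupon for 6-monthly testing.

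Section 14 counts four self-tests for a fully adherent participant, that is, one first kit and three repeats. Repeat testing is a secondary endpoint in its own right in sections 7 and 14.

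**The concern.** A recruitment coupon goes to a peer who is not yet enrolled. A repeat coupon goes to someone who has already enrolled, tested and returned a result, and who is being reminded. Redemption of the first shows whether peer referral brings people to a pharmacy; redemption of the second shows whether they come back. The primary definition does not say which it measures. Taken literally, repeat kits enter the numerator and repeat coupons the denominator.

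The same peer recruitment could then yield quite different primary results depending on retention, or on which reading an analyst adopts. The paper versus electronic comparison is exposed as well, because repeat coupons enter those strata in proportions that have nothing to do with how peers respond to either format.

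**Working it through.** **The plan's own figure.** Section 14 takes p = 0.70 and n = 1500: 1.96 × √(0.70 × 0.30 / 1500) = 2.32 points, which agrees with the stated 2 to 2.5. I use it only as the yardstick for the shifts below.

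**Inputs from the protocol.** At most 1500 participants (section 1); 15 initial seeds and 10 coupons per seed or participant (section 5); up to three repeats (section 14); planning uptake 70% (section 14); HIV prevalence 2.3% in MSM and 5.9% in TGW (section 3).

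**Assumptions.** The protocol gives no redemption rate for repeat coupons, so r, the share redeemed per round, is varied from 0 to 100%. Each round issues one coupon to everyone who tested in the round before. Base uptake is taken at two values:

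- About 10%, which follows if all 1500 participants hand on 10 coupons: 1500/15,000.
- The planning value of 70%, which corresponds to 1500/0.70 = 2143 recruitment coupons.

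**Formula.** With F first kits and C recruitment coupons, repeat coupons are R = F(1 + r + r²) and repeat kits are rR. The pooled ratio is (F + rR)/(C + R). This is a weighted average of base uptake F/C and r, so it rises when r exceeds base uptake and falls when r is below it.

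| r per round | Base 10% (C = 15,000) | Base 70% (C = 2143) |
|---|---|---|
| 0% | 1500/16,500 = 9.1% | 1500/3643 = 41.2% |
| 50% | 2812.5/17,625 = 16.0% | 2812.5/4768 = 59.0% |
| 70% | 3799.5/18,285 = 20.8% | 3799.5/5428 = 70.0% |
| 100% | 6000/19,500 = 30.8% | 6000/6643 = 90.3% |

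Peer recruitment is identical down each column.

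**Allowing for reactive results and non-return.** Expected reactive share: (1000 × 2.3% + 500 × 5.9%)/1500 = 52.5/1500 = 3.5%, leaving about 1447 non-reactive. Counting the 15 seeds within the 1500, base uptake is 1485/15,000 = 9.9%. If 80% upload a result and 60% of those redeem in each round (assumed), repeat coupons are 1158 + 556 + 267 = 1981 and repeat kits 695 + 333 + 160 = 1188. Pooled: (1485 + 1188)/(15,000 + 1981) = 15.7%. With full adherence, 3 × 1447 = 4341 of each: (1485 + 4341)/(15,000 + 4341) = 30.1%.

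**Coupon-type strata.** Take the 80%/60% scenario and assume recruitment coupons are half paper and half electronic, with equal 9.9% uptake.

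- All repeat coupons electronic: paper 742.5/7500 = 9.9%; electronic (742.5 + 1188)/(7500 + 1981) = 20.4%.
- Repeat coupons split evenly: each stratum (742.5 + 594)/(7500 + 990.5) = 15.7%. There is no spurious difference, but both are off the peer figure.
- All electronic, one issued to each of the 1447 and none redeemed: electronic 742.5/(7500 + 1447) = 8.3%, below paper.

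**Restricted ratio.** First kits on recruitment coupons over recruitment coupons stays at 9.9% to 10.0% in the low-base case and at 70% in the planning case, whatever r is.

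**The case against.** The best defence is that the text is silent on repeats and a recruitment-only reading is natural. Coupons are distributed only where the protocol speaks of peers; repeat coupons are provided, received or downloaded. Repeat testing also has its own endpoint. This makes the intention plausible, but it does not settle the ratio. The numerator is self-tests delivered, and the data-collection and monitoring text in section 13 reconciles delivered kits with entries and pharmacy stock without distinguishing first from repeat. If only the denominator is confined to peer coupons, repeat kits remain on top: at the 70% base with 50% redemption, 2812.5/2143 = 131%, which is not a proportion.

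A second defence is that the primary objective is feasibility of pharmacy delivery, and repeat kits are delivery too. That is fair, but it supports reporting repeat delivery separately rather than merging two populations of coupons in one ratio.

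Third, this is a descriptive pilot with no success threshold tied to the ratio, and each coupon carries a unique code, so first and repeat kits can probably be told apart at analysis. This stands and limits the harm. It does not say which ratio is the primary one.

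A reader might infer that retention alone will double or triple the reported uptake. The documents do not support that as an expectation. With a base of 10%, doubling needs about 67% redemption in every round and tripling about 98%. If the last wave's coupons are left out, a 70% redemption chain stopped at 1500 gives a base of 1485/8550 = 17.4% and a ceiling of about 2.6 times. At 70% the ceiling is 90.3/70 = 1.29 times. Data collection from August 2023 to April 2025 spans about 21 months (the protocol labels it 18), so late enrollees cannot complete three repeats. With even enrolment over an assumed 6 months and full redemption, the multiplier on a 10% base is about 2.5 to 2.8.

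A reader might also infer that electronic coupons will necessarily look better. Section 5 allows either format by preference, the half-and-half split is fixed only for seeds, and low redemption would push the electronic figure down.

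**Conclusion.** The point holds as a defect of definition. The primary ratio, as worded in sections 1, 7 and 14, does not distinguish peer uptake from retention, and no stratum separates them. The protocol does not state that repeats are counted; it fails to exclude them.

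The size is conditional. With base uptake near 10%, the pooled figure lies between about 9% and 30%, and is about 16% either at 50% redemption per round or with 80% upload and 60% redemption. At the 70% planning value it lies between about 41% and 90%, and equals 70% only when repeat redemption is also 70%. The ends of both ranges are extremes, but even the 50% row moves the planning value by 11 points, well beyond the stated precision. The direction cannot be known in advance. Contamination of the paper and electronic strata is certain in kind if repeats are pooled; its amount depends on a coupon format on which sections 5, 8 and 9 differ.

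**What to change.** - In sections 1, 7 and 14, define the primary endpoint as first kits delivered on recruitment coupons divided by recruitment coupons distributed, overall and by gender and coupon type.
- Record a purpose, recruitment or repeat, against each unique QR code when it is issued.
- Report repeat coupons and repeat kits only under the 6-monthly testing endpoint.
- Reconcile sections 5, 8 and 9 on the format of the repeat coupon.

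The cost is a change of wording and one data field on codes that already exist. The headline uptake may be lower than a pooled figure would have been. The flag is best set before coupons go out, since purpose recorded at issue is safer than purpose inferred later.

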with the important details about the study. Once consent to the study, the seed is provided with two types of coupons for HIVST kit at partner pharmacy: 1- 5 electronic coupons (e-coupons) consisting of a pictured unique anonymous QR code and identifier and address of partner pharmacies 2- 5 paper coupons consisting of a printed unique anonymous QR code, identifier and address of partner pharmacies. The seeds will provide paper- and e-coupons to their networks physically and via social media, messaging and calling applications such as Twitter, Whatapp and Telegram (e-coupons). For online application and social media, a peer could be reached by chat or call.

When the participant arrives in a partner pharmacy, the coupon (unique QR code with identifier) will be scanned by the pharmacist prior to the free delivery of HIV self-test. Community workers (CWs) will be then alerted by the pharmacist for study visits to participant directly at the dedicated space at the pharmacy. During the visit with CW, participant will:

- Receive the information about the study
- Receive an ID
- Check for eligibility criteria
- Be requested for his/her consent to participate in the study and to different specific consents as receiving funds, being recontacted by phone and participation in FGD
- Fill in the detailed e-CRF for sociodemographic status, sexual behaviors, utilization of dating application, substance use, knowledge about PrEP and willingness to pay for HIV self-testing by using Tablet with the eventual assistance from a community worker
- Receive the information on HIV self-testing instructions, list of partner pharmacies, helpline phone number, location of the 2 partners ART sites, location of the HIV clinics with prevention services and PrEP delivery availability
- Be provided one free HIV self-testing kit delivered
- Receive the link of the external website to performance HIV test, interpret and send the HIV test result, receive necessary information and in case of non-reactive, to receive another coupon for 6-monthly test during 18 months
- Receive 10 (paper or electronic) coupons to distribute to peers
- Be asked if the participant would agree to be recontacted for an eventual participation in a focus group

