Incentives will be provided in two steps for participants to encourage them to return the results of HIVST and recruit their peers. In step one, each participant will receive 2 USD for returning the HIVST result successfully to the provided link. In step two, an amount of 1 USD will be provided for each recruited peer. This amount was decided as a balance between feasibility (encouragement) and sustainability of the strategy (not too high for possible scaling-up).

In case of any issue for tablet use or HIVST kit use, helpline phone number will be available. One dedicated community worker funded by the study will be in charge to manage helpline service.

Intervention after delivering HIV test result

In case of reactive HIV test, the participant could join immediately one research team by hotline or messages on the website that will provide support and orientation. After 1 week, contact with the participant will be done by phone by the research team (if the participant gave consent) to confirm the linkage to one of the partner ART sites. The linkage between participants and HIV clinics will be done by the initial QR code.

Version 1.1 du 18/04/2022

If the linkage to confirmatory testing and/or care is not confirmed, we will propose to participant additional help of a community worker.

In case of non-reactive test, the participant could download in the external website one electronic coupon (QR code) to repeat the HIV test 6 month later. Participants will be informed on the external website about the possibilities to join the pilot PrEP program in Chhouk Sar clinic in Phnom Penh.

Qualitative assessment

After 6 months, a qualitative assessment will be conducted to evaluate acceptability and appropriateness of the intervention. Qualitative assessment will be done by focus groups. Focus groups will be conducted in 3 specific populations: MSM, TGW and pharmacists. For each population of MSM and TGW, a qualitative sample will be selected in order to capture different profiles according to sex behaviors and demographic and socioeconomic characteristics.

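### The linkage endpoints count any ART site and any PrEP service, but the described data collection is built around participating centres, so linkage elsewhere may be missed and measured linkage can only fall

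*Protocol*

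**What the plan says.** **Endpoints.** Protocol Section 7 lists "Proportion of MSM/TGW with positive HIV self-tests linked to an ART site" and "Proportion of negative MSM/TGW linked to PrEP services". Section 14 analyses both as percentages with 95% confidence intervals, stratified by gender. Neither section limits the count to partner or participating sites.

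**Centres.** Section 5 (Study overview) says that "Several ART sites/HIV clinics particularly in charge of key populations will be specifically selected as participating centers", so that linkage information can be collected for positive and negative participants. Sections 8 and 9 give the initial QR code as the key between participant and clinic. Section 16.4 makes the study code the only identifier, and the database holds no link to a name.

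**Contact after a reactive test.** Section 8 states that after one week "contact with the participant will be done by phone by the research team to confirm the linkage to one of the partner ART sites". Section 9 repeats this and makes the call conditional on consent. Its loss-to-follow-up text uses the same partner-site criterion as a trigger for phoning.

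**Contact after a non-reactive test.** Section 8 says the external website will tell participants about the "possibilities to join the pilot PrEP program in Chhouk Sar clinic in Phnom Penh". Section 9 also gives every participant the locations of HIV clinics that offer prevention and PrEP. The loss-to-follow-up text provides for a call when a 6-month test is missed, but does not mention PrEP.

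**The concern.** What is to be estimated is wider than what is set up to be observed. Someone with a reactive test who seeks confirmation or care at a non-participating clinic, or who attends a participating clinic without presenting the QR code, leaves no trace in the clinic matching. The one-week call, as worded, does not ask about other sites. For PrEP, the participating centres are the only data source described.

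The error has one direction: unobserved linkage can lower the measured proportion but not raise it. Each endpoint serves a secondary objective in Section 4. The protocol itself stresses anonymity for these populations (Section 3), so attendance outside the study's channels is conceivable, although nothing in the document says how common it would be. The matter concerns what is collected, and a later analysis plan cannot recover an answer to a question that was never asked.

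**Working it through.** **1. The protocol's own precision figure.** Section 14 gives one, for kit uptake: 1.96 × √(0.70 × 0.30 / 1500) = 2.32 points, inside the stated ±2–2.5%. None is given for linkage, and this point does not depend on the uptake figure.

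**2. Endpoint against data source.**

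| | Endpoint (Sections 7, 14) | Described source (Sections 5, 8, 9) | Not covered |
|---|---|---|---|
| Reactive | any ART site | QR matching at participating centres; consent-dependent one-week call about partner ART sites | linkage elsewhere, or without the QR code, unless volunteered in the call |
| Non-reactive | PrEP services | participating centres | PrEP attendance elsewhere, or without the QR code; no contact asking about PrEP is described |

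**3. Number of reactive results.** Inputs: 1000 MSM and 500 TGW (Section 14); prevalence 2.3% and 5.9%, presented as the latest key-population data (Section 3). Section 3 also lists 37% for transgender people in Phnom Penh from a regional source, which is not used here.

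- Ceiling at these prevalences, first test, false reactives left aside: 1000 × 0.023 + 500 × 0.059 = 23 + 29.5 = 52.5, about 52.
- Known positives are not eligible (Section 1). If the national 82% awareness figure (Section 3) applied to these groups, which is an assumption, the proportion infected among those eligible would be p(1 − a)/(1 − pa):
  - MSM: 0.023 × 0.18 / (1 − 0.023 × 0.82) = 0.00422, or 4.2 people per 1000.
  - TGW: 0.059 × 0.18 / (1 − 0.059 × 0.82) = 0.01116, or 5.6 people per 500.
  - Total: 9.8, about 10.

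One missed person moves the overall estimate by 1/52 = 1.9 points at the ceiling, or 1/10 = 10 points at the lower count.

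**4. Size of the loss.** Let L be true linkage and s the share of linkers who go elsewhere. If they are scored as not linked, measured linkage is L(1 − s) and the loss is L × s. The protocol gives neither L nor s, so both are assumptions.

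| L | s = 5% | s = 10% | s = 20% | s = 30% |
|---|---|---|---|---|
| 60% | 57.0 | 54.0 | 48.0 | 42.0 |
| 70% | 66.5 | 63.0 | 56.0 | 49.0 |
| 80% | 76.0 | 72.0 | 64.0 | 56.0 |
| 90% | 85.5 | 81.0 | 72.0 | 63.0 |

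(Measured linkage, %.) The loss runs from 0.60 × 0.05 = 3 points to 0.90 × 0.30 = 27 points.

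**5. Against sampling error.** At L = 80% the 95% half-width is 1.96 × √(0.16/52) = 10.9 points, or 1.96 × √(0.16/10) = 24.8 points. For PrEP, with about 1450 non-reactive participants and an assumed 10% linkage, it is 1.96 × √(0.09/1450) = 1.5 points, while s = 20% costs 0.10 × 0.20 = 2 points.

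**The case against.** The strongest reply is that these are descriptive secondary endpoints in a feasibility pilot whose primary endpoint is kit uptake. No test or threshold rests on them, the centres are chosen because they serve key populations, and a live call can bring out linkage elsewhere whatever its stated purpose. Sections 8 and 9 then offer a community worker when linkage to confirmatory testing or care is not confirmed, and that sentence is not limited to partner sites. This stands as a limit on importance, and it means some non-partner linkage among reactive participants would probably surface. It does not close the gap: the call needs consent, nothing says that linkage elsewhere is recorded, and no counterpart for PrEP is described.

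Several stronger readings are tempting but not supported:

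- **That people who link elsewhere are recorded as not linked.** The protocol gives no coding rule. They could be coded unknown, or linked by self-report, and such rules may sit in an analysis plan that is not shown.
- **That negatives are never called.** Some are, when they miss the 6-month test. What is absent is a described question about PrEP.
- **That the number of sites is contradictory.** Section 5 speaks of several ART sites and HIV clinics together. Section 9 mentions the "location of the 2 partners ART sites" and lists the prevention clinics separately. Two ART sites plus other clinics can be several, so this is at most an ambiguity. Naming one PrEP programme on the website while listing several clinics is no conflict either.
- **That each gender stratum will hold 23 to 30 reactive participants.** Those are ceilings that ignore the exclusion of known positives. With about 10 in total, sampling error of about ±25 points would exceed most of the assumed loss.

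**Conclusion.** The mismatch is real and modest in reach. The endpoints cover any ART site and any PrEP service; the described ascertainment covers participating centres, plus a consent-dependent call with a partner-site purpose for reactive participants. Followed as written, the plan may miss linkage elsewhere, and any resulting error is downward. It is clearest for PrEP.

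The size cannot be taken from the protocol. The 3–27 point range rests on assumed linkage, an assumed share going elsewhere, and scoring those people as not linked; it shows what could happen and does not predict it. The count of about 10 reactive results also assumes that national awareness applies to these groups. The primary endpoint is unaffected. The change is worth making because it is cheap and cannot be made after data collection.

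**What to change.** 1. In the one-week call already planned, ask about linkage to any confirmatory, ART or care site, and record where.
2. On the web page where the 6-month coupon is downloaded, add one question on attending any PrEP service since the last test. A download straight after the first result may come too early to show attendance, so the answers at later downloads carry most of the information.
3. Report two figures for each endpoint: QR-verified linkage at participating sites, and verified plus self-reported linkage at any site. Show participants with unknown linkage separately.
4. If the questions are not added, restate both endpoints in Sections 1, 7 and 14 as linkage to participating sites.
5. List the participating ART sites and PrEP clinics once, and use the same terms throughout.

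The cost is one question in an existing call, one on an existing page, and one more line per endpoint in the report. The downside is that self-report is less certain than QR verification, which is why the two figures stay apart. People who decline recontact or do not return to the website remain unknown.
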